8.1.2 Primary analysis of the primary efficacy variable

The primary efficacy variable, time to event during the 166-day Treatment Period, will be evaluated using a Cox proportional hazards regression model (Cox, 1972), with an effect for treatment, stratifying for the subjects' Baseline PGTCS frequency (\leq 2 per 28 days vs >2 per 28 days in the Combined Baseline Period) and age at informed consent (\geq 4 to <12 years of age, \geq 12 to <18 years of age vs \geq 18 years of age). The analysis will use the stratification factors from IRT and pooled as described in Section 4.9.

The hypothesis for the assessment of primary efficacy variable (time to event) is as follows:

$$H_0$$
: $\beta=0$

Versus

where β is the coefficient of an independent variable representing the treatment effect in the model. The hazard function is represented by

$$h(t,X) = h_0(t) \exp(\sum_{j=1}^p \beta_j X_j)$$

where x_j is the collection of independent variables and $h_0(t)$ is the baseline hazard at time t. For the null hypothesis, the testing will be 2-sided with an α =0.05; the p-value will be presented. The

assumptions of proportional hazards will also be assessed graphically (e.g. log (log S) plot vs time, empirical score process) for any departure; non-proportionality is not expected when using a stratified Cox model. Depending on the departure from proportional hazards, a sensitivity analysis (e.g. piecewise proportional hazards, time-varying coefficient, restricted mean survival) may be performed.

The stratified hazard ratio (HR) will be calculated using the placebo arm as the reference group. The 95% CI for the HR will also be reported.

Additionally, a Kaplan-Meier (KM) plot for time to event as well as the KM estimate for the median time to event and 95% CI will be provided. If the median time is not estimable, then the 25th percentile and 95% CI will be provided. The number of events will be reported by treatment group for the Titration Period, first 12 Weeks, and Treatment Period as well as the % of subjects who were censored in the analysis.

8.1.3 Secondary analyses of the primary efficacy variable

The summary of time to the event during the 166-day Treatment Period will be presented by all subgroup for the FAS. A KM plot for time to second PGTCS by all subgroups will also be provided.

8.1.4 Supportive and sensitivity analyses of the primary efficacy variable

The following additional sensitivity analyses on the primary efficacy endpoint will be conducted in order to assess the effect of dropouts, important protocol deviations, and operational bias on the primary endpoint:

- Repeat the primary efficacy analysis using the PPS.
- Repeat the primary efficacy analysis using all PGTCS data (ie, all reported events after the date of the 125th event) through each subject's first 166 days of treatment, on the FAS.
- Repeat the primary efficacy analysis using the FAS, except all subjects who prematurely discontinue due to lack of efficacy, consent withdrawn, or lost to follow-up will be analyzed as treatment failures (ie, events at the time of discontinuation).
- Repeat the primary efficacy analysis using the FAS, except all subjects who prematurely discontinue due to lack of efficacy or AEs only will be analyzed as treatment failures.
- Repeat the primary efficacy analysis using the FAS, comparing the event rates prior to vs after each interim analysis to examine possible operational bias due to unblinding.
- Repeat the primary efficacy analysis using the FAS, except all subjects who prematurely discontinue after their 1st PGTCS will be analyzed as treatment failures.

8.2 Statistical analysis of the secondary efficacy variables

Provided that the primary efficacy endpoint is statistically significant, a gatekeeping strategy will be used to test the key secondary efficacy variable. Analyses of all other secondary efficacy variables will be descriptive in manner only. Any p-values or confidence limits provided other than those for the primary efficacy analysis of the primary efficacy variable (as described in Section 8.1.2) and the analysis of the key secondary efficacy variable will be exploratory only.

8.2.1 **Derivations of secondary efficacy variables**

8.2.1.1 Variable: Seizure freedom for PGTCS for the 166-day Treatment

A subject will have seizure freedom from PGTCS for the 166-day Treatment Period if the subject completed the Treatment Period and reported zero PGTCS or "not done" for all days during the 166-day Treatment Period. Ongoing subjects who are seizure-free from PGTCS and date of the 125th event do not have seizure-freedom from PGTCS unless the from PGTCS for 166 days.

8.2.1.2 Variable. To

For PGTCS, how the time to first PGTCS is calculated is described in Section 3.2.3. Censoring of subjects for this analysis will be as described in Section 3.2.4.

If a day is marked in the CRF as "not done", it will be assumed that no seizures occurred on that seizure diary day.

Analysis of secondary efficacy variables 8.2.2

Analyses of secondary efficacy variables will be performed for the FAS.

Analysis: Seizure freedom for PGTCS for the 166-day Treatment 8.2.2.1 Period

Analysis of the key secondary efficacy variable, seizure freedom for PGTCS for the 166-day Treatment Period, will be evaluated using an extended Mantel-Haenszel testing procedure which takes into account that the subjects were initially stratified for the subjects' Baseline PGTCS frequency (\leq 2 per 28 days vs \rightarrow 2 per 28 days in the Combined Baseline Period) and age at informed consent (≥ 4 to ≤ 12 years of age, ≥ 12 to ≤ 18 years of age vs ≥ 18 years of age). The analysis will use the stratification factors from IRT and pooled as described in Section 4.9.

The hypothesis for the assessment of the key secondary efficacy (PGTC seizure-freedom) is as follows:

$$H_0$$
: $S(t=166)_{LCM} = S(t=166)_{PBO}$

Versus

$$H_1$$
: $S(t=166)_{LCM} \neq S(t=166)_{PBO}$

Where S(t=166) is the cumulative rate of subjects remaining seizure-free from PGTCS for 166 days

Estimation of treatment difference:

KM methods will be used to estimate the proportion of subjects remaining seizure-free from PGTCS at Day 166. The estimate for the difference in Day 166 seizure-freedom from PGTCS will be adjusted for subjects' Baseline PGTCS frequency (≤2 per 28 days vs >2 per 28 days in the Combined Baseline Period) and age at informed consent (≥ 4 to ≤ 12 years of age, ≥ 12 to ≤ 18 years of age vs >18 years of age). The estimate for the stratified difference in proportion of

subjects who are seizure-free from PGTCS on LCM vs PBO and a corresponding 95% two-sided confidence interval (CI_{LCM-PBO}) will be produced using mantel Haenszel methods (LaVange et al, 2005). The statistical methodology is expressed as follows:

$$d = \sum_{h=1}^{6} w_h(S_{h1} - S_{h2})$$

Where Shi=KM estimate of 166-day seizure freedom from PGTCS for treatment i (1=LCM and 2=PBO) in stratum h (1= \leq 2 per 28 days Baseline PGTCS frequency and \geq 4 to \leq 12 years of age, $2 = \le 2$ per 28 days Baseline PGTCS frequency and ≥ 12 to < 18 years of age, $3 = = \le 2$ per 28 days 0Baseline PGTCS frequency and ≥18 years of age, 4=>2 per 28 days Baseline PGTCS frequency and \geq 4 to <12 years of age, 5=>2 per 28 days Baseline PGTCS frequency and \geq 12 to <18 years of age and 6= >2 per 28 days Baseline PGTCS frequency and ≥18 years of age and $\mathbf{w_h} = \{ (\mathbf{n_{h1}} * \mathbf{n_{h2}}) / (\mathbf{n_{h1}} + \mathbf{n_{h2}}) \} / \sum_{h=1}^{6} \{ (\mathbf{n_{h1}} * \mathbf{n_{h2}}) / (\mathbf{n_{h1}} + \mathbf{n_{h2}}) \} \}$

where n_{hi} is the number of subjects in I treatment group and stratum h. The variance of d is calculated as $Var(d) = \sum_{h=1}^{6} w_h^2 \{Var(S_{h1}) + Var(S_{h2})\}$ where $Var(S_{h1})$ and $Var(S_{h2})$ are the Greenwood estimates of variance for S_{h1} and S_{h2} .

The stratified proportion of subjects remaining seizure free from PGTCS for at least 166 days in each treatment group and the associated variance are derived as follows using Mantel Haneszel methods:

The KM estimate for the LCM 166-day seizure-freedom from PGTCS rate is calculated as $S_1 = \sum_{h=1}^6 w_h S_{h1}$

The KM estimate for the PBO 166-day seizure-freedom from PGTCS rate is calculated as $S_2 = \sum_{h=1}^6 w_h S_{h2}$

 $S_2 = \sum_{h=1}^6 w_h S_{h2}$ The variance is S1 is calculated as $Var(S_1) = \sum_{h=1}^6 w_h^6 Var(S_{h1})$

The variance of S2 is calculated as $Var(S_2) = \sum_{h=1}^{6} w_h^6 Var(S_{h2})$

In order to assess superiority, 2-sided testing with α =0.05 will be used. The superiority test statistic, $Q=d^2/Var(d)$ will be assessed by a chi-square distribution with 1 degree of freedom. This statistic is referred to as the row mean score statistic" when using Proc Freq.

The number and percentage of subjects who experience a PGTCS or censoring and the KM seizure-free rate from PGTCS (and 2-sided 95% CI) by Day 166 will be presented by treatment group for each stratum and overall. The stratified seizure-freedom rate from PGTCS (and 2-sided 95% CI) at Day 166 for each treatment group and the difference between treatment groups will be presented. A Kaplan-Meier plot will be presented by treatment group for each stratum and overall.

For the gatekeeping strategy, if the primary endpoint is statistically significant at the 5% level, then the key secondary efficacy endpoint will also be assessed at the 5% significance level. If the will be exploratory only.

8.2.2.2 primary endpoint fails to reach statistical significance, then the key secondary efficacy endpoint

Analysis: Time to first PGTCS during the 166-day Treatment Period

Time to the first PGTCS during the 24-week Treatment Period will be evaluated using a Cox proportional hazards regression model (Cox, 1972), with an effect for treatment, stratifying for the subjects' Baseline PGTCS frequency (\le 2 per 28 days vs \rightarrow 2 per 28 days in the Combined

Baseline Period) and age at informed consent (≥ 4 to ≤ 12 years of age, ≥ 12 to ≤ 18 years of age vs \ge 18 years of age). The analysis will use the stratification factors from IRT and pooled as described in Section 4.9.

$$H_0$$
: $\beta=0$

 $H_1: \beta \neq 0$ where β is the coefficient of an independent variable representing the treatment effect in the model. The hazard function is represented by $h(t,X) = h_0(t) \exp(\sum_{i=0}^{p} \rho_i v_i)$ where x_i is the collision.

$$h(t,X) = h_0(t) \exp(\sum_{j=1}^{p} \beta_j X_j)$$

where x_i is the collection of independent variables and $h_0(t)$ is the baseline hazard at time t. For the null hypothesis, the testing will be 2-sided with an α =0.05. The assumptions of proportional hazards will also be checked using the same approach as for the primary efficacy endpoint.

The stratified HR will be calculated using the placebo arm as the reference group. The 95% CI for the HR will also be reported.

Additionally, a KM plot for time to 1st PGTCS as well as the KM estimate for the median time to 1st PGTCS and 95% CI will be provided. If the median time is not estimable, then the 25th percentile and 95% CI will be provided. The number of 1st PGTCS will be reported by treatment group for the Titration Period, first 12 Weeks, and Treatment Period as well as the % of subjects who were censored.

Analysis of seizure related other efficacy variables 8.3

All seizure data recorded during the treatment period will be summarized and listed for the seizure related other efficacy variables. Analyses of seizure-related other efficacy variables will be performed for the FAS. For absence seizure analyses, this analysis population will be further restricted to the subset of subjects who reported a history of absence seizures or reported absence seizures during baseline or the 24-week treatment period. For myoclonic seizure analyses, this analysis population will be further restricted to the subset of subjects who reported a history of myoclonic seizures or reported myoclonic seizures during baseline or the 24-week treatment period.

©Derivations of seizure related other efficacy variables 8.3.1

Variable: PGTCS frequency per 28 days

In order to account for potential differences in the durations of the study periods for individuals, PGTCS data will be normalized to 28 days.

The 28-day PGTCS frequency (SF) will be calculated for the Combined Baseline and Treatment Periods as:

SF =

(# PGTCS in the relative period/# days in relative period with evaluable PGTCS data)*28

The percent change (PCH) in PGTCS frequency per 28 days from the Combined Baseline (CB) to the appropriate analysis period (T) is defined as:

$$PCH = [(SFT - SFCB) / SFCB] \times 100$$

or variations thereof where SFT corresponds to the 28-day PGTCS frequency during the relative period and SFCB corresponds to the 28-day Combined Baseline PGTCS frequency. PCH is calculated for 6-week Titration Period, first 12 weeks of the Treatment Period and the 24-week Treatment Period.

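### Per-arm variances of the stratified 166-day seizure-freedom rates raise the weights to the 6th power instead of squaring them, so their 95% CIs come out several-fold too narrow

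*SAP*

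**What the plan says.** Section 8.2.2.1 of the SAP sets out the analysis of the key secondary endpoint, freedom from PGTCS at Day 166. (The quoted formulas below are cut just before their closing brackets.)

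- **Weights.** Mantel-Haenszel weights, normalised to sum to 1: "w_h} = \{ (\mathbf{n_{h1}} * \mathbf{n_{h2}}) / (\mathbf{n_{h1}} + \mathbf{n_{h2}}) \} / \sum_{h=1}^{6".
- **Per-arm rate.** Linear in the weights, shown here for placebo: "The KM estimate for the PBO 166-day seizure-freedom from PGTCS rate is calculated as $S_2 = \sum_{h=1}^6 w_h S_{h2". Lacosamide has the same form.
- **Variance of the difference d.** Squared weights: "Var(d) = \sum_{h=1}^{6} w_h^2 \{Var(S_{h1}) + Var(S_{h2".
- **Variance of each arm's rate.** Sixth power: "The variance is S1 is calculated as $Var(S_1) = \sum_{h=1}^6 w_h^6 Var(S_{h1" for lacosamide and "The variance of S2 is calculated as $Var(S_2) = \sum_{h=1}^{6} w_h^6 Var(S_{h2" for placebo.
- **Test.** "Q=d^2/Var(d)$ will be assessed by a chi-square distribution with 1 degree of freedom".
- **Output.** "The stratified seizure-freedom rate from PGTCS (and 2-sided 95% CI) at Day 166 for each treatment group" is to be presented, together with the difference between arms.

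**The concern.** An arm's rate is a fixed-weight sum of independent stratum estimates, so each stratum variance must be multiplied by the square of its weight. The sixth power does not follow from the definition of the rate, and it conflicts with the variance of the difference given a few lines earlier.

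The per-arm variances have one planned use, the 95% CI around each arm's stratified rate. This is the only endpoint besides the primary that is formally tested, so those intervals are likely to be quoted. Programmed as written, the results table would show very narrow arm intervals beside a correctly wide interval for the difference. The two arm intervals could be clearly separate while the difference is not significant. A second programmer validating against the SAP would reproduce the error.

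**Working it through.** **1. Algebra, from the SAP's own definitions.** With `S_i = Σ w_h S_hi` and independent strata, `Var(S_i) = Σ w_h² Var(S_hi)`. Also `d = Σ w_h (S_h1 − S_h2) = S_1 − S_2`. The arms are independent, so `Var(d) = Var(S_1) + Var(S_2)`. Squared weights reproduce the SAP's Var(d) exactly. Sixth powers cannot do so unless a single stratum carries all the weight.

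**2. Direction.** The weights sum to 1, so with two or more strata every w_h is below 1 and w_h⁶ is below w_h². Section 4.9 pools age categories within each baseline-frequency level and never across levels. At least two strata therefore remain if both levels contain subjects.

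**3. Size with a common rate.** From the SAP: 1:1 allocation and at most 250 subjects, so 125 per arm. Assumed: the weights, rates of 30% and 15%, and binomial variance (no censoring). With equal allocation within strata, n_hi = 125 w_h and Var(S_hi) = p(1−p)/(125 w_h). Then:

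- squared weights: Var(S_i) = p(1−p)/125, because Σ w_h = 1
- sixth powers: Var(S_i) = [p(1−p)/125] × Σ w_h⁵
- the SE is too small by a factor of 1/√(Σ w_h⁵)

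With squared weights, Var(S_1) + Var(S_2) = 0.21/125 + 0.1275/125 = 0.00168 + 0.00102 = 0.00270, which equals Var(d). The 95% half-widths are 1.96 × √0.00168 = 8.0 points and 1.96 × √0.00102 = 6.3 points.

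| Assumed weights | Σ w⁵ | SE too small by | Half-width at 30% (correct 8.0 points) | Simulated coverage of nominal 95% CI |
|---|---|---|---|---|
| six equal | 6 × (1/6)⁵ = 1/1296 | 36 | 0.2 | 8% |
| .05/.12/.45/.04/.09/.25 | 0.0195 | 7.2 | 1.1 | 23% |
| .2/.5/.1/.2 | 0.0319 | 5.6 | 1.4 | not simulated |
| two equal | 2 × (1/2)⁵ = 1/16 | 4.0 | 2.0 | not simulated |
| .04/.12/.64/.01/.04/.15 | 0.1075 | 3.1 | 2.6 | 44% |
| .8/.2 | 0.328 | 1.75 | 4.6 | 73% |
| .9/.1 | 0.590 | 1.3 | 6.2 | not simulated |
| one stratum | 1 | 1.0 | 8.0 | not simulated |

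With squared weights, coverage was about 94% in every simulated case (20,000 runs each). For six equal strata the sixth-power formulas give Var(S_1) + Var(S_2) = 0.000002 against Var(d) = 0.002700.

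**4. Size with different rates by baseline frequency.** Assumed: 30% freedom at ≤2 PGTCS per 28 days and 6% at >2, so p(1−p) is 0.21 and 0.0564. The factor is √(Σ w v / Σ w⁵ v), where v is p(1−p).

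- Six strata at 2/10/48/2/8/30%: Σ w v = 0.60 × 0.21 + 0.40 × 0.0564 = 0.1486 and Σ w⁵ v = 0.00549, a factor of 5.2.
- Pooled to 12/48/40%: 0.1486 / 0.00593, a factor of 5.0.
- Two strata at 60/40%: 0.1486 / 0.0169, a factor of 3.0.
- Two strata at 80/20%: 0.1793 / 0.0688, a factor of 1.6.

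**5. Kaplan-Meier simulation.** This used the six-stratum shares of step 4, an assumed N of 242, 15% dropout and 3,000 trials per scenario. The mean SE of an arm's rate was 0.036-0.046 with squared weights and 0.007-0.009 with sixth powers. Coverage was 93-94% and 27-30% respectively. As a rough check, a factor of 5.2 implies coverage of 2Φ(1.96/5.2) − 1 = 29%.

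**The case against.** **Nothing inferential uses these variances.** This is correct. The test, the CI of the difference and the gatekeeping step rest on Var(d), which has the right exponent. Only two descriptive intervals are wrong, and the treatment comparison cannot change.

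**It is a typographical slip.** Probably so: the upper summation limit of 6 seems to have been repeated on the weight, and the correct pattern stands a few lines above. A careful programmer may notice. The SAP nevertheless prescribes the sixth power for both arms.

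**It could be a PDF-reading error.** This is unlikely. The exponent 6 appears for both arms in Section 8.2.2.1 and again for both arms in the revised text reproduced in Section 13.3.2.1, while Var(d) shows exponent 2 in both places.

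**The size is not a property of the SAP.** Fair. It depends on weights the SAP does not state and on pooling under Section 4.9. Six equal strata is an extreme illustration. In the step 4 scenario with N = 242, expected seizure-free counts at >2 PGTCS per 28 days are about 0.3, 1.2 and 4.4 by age, and about 1.5 in the youngest group at ≤2. Pooling would therefore apply and give the 12/48/40% split. The factor then falls only from 5.2 to 5.0. It approaches 1 only when one stratum dominates.

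**Conclusion.** The two per-arm variance formulas are wrong as written and contradict the variance of the difference in the same section. The contradiction and its direction follow from the SAP alone; the size rests on assumed weights and rates. The SE is understated about 3-fold to 7-fold for the unequal four- and six-stratum splits examined and 36-fold for six equal strata. With two strata the factor is 4.0 for an equal split, 3.0 for 60/40, 1.6 to 1.75 for 80/20 and 1.3 for 90/10. Per-arm 95% CIs for the key secondary endpoint would therefore usually be several-fold too narrow. The conclusion on treatment effect is not at risk, but the planned arm-level intervals would be invalid and should be corrected before programming.

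**What to change.** In Section 8.2.2.1, replace the sixth power by the square in both formulas, so that `Var(S_i) = Σ w_h² Var(S_hi)` for i = 1 and 2. This is the whole remedy. A useful but optional safeguard is a programming check that Var(S_1) + Var(S_2) equals Var(d). The cost is two exponents in the SAP, with no change to data, design, alpha or the planned test.

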8.3.1.2 Variable: Days with seizures per 28 days

The number of days with absence seizures per 28 days will be calculated separately for the Prospective Baseline and the Treatment Period as:

D = ([# days with absence seizures in the relative period] / [# days in relative period with evaluable seizure data]) * 28.

Similarly, the number of days with myoclonic seizures per 28 days will be calculated.

The percent change (PCH) in days with absence seizures per 28 days from the Prospective Baseline (B) to the appropriate analysis period (T) is defined as:

$$PCH = [(DT - DB) / DB] \times 100$$

where DT corresponds to the number of days with absence seizures per 28 days during the relative period and DB corresponds to the number of days with absence seizures per 28 days during the Prospective Baseline Period. If DB is zero, then PCH will be missing and any such subjects will be excluded from the percent change summary. PCH will be calculated for the 6week Titration Period, first 12 weeks of the Treatment Period and the 24-week Treatment Period.

Similarly, the percent change in the number of days with myoclonic seizures per 28 days from the Prospective Baseline Period will be calculated.

Variable: Seizure-free status 8.3.1.3

A subject will have seizure-free status for PGTCS=ves for the Treatment Period if the subject completed the Treatment Period (with a minimum 166 days) and reported zero PGTCS or "not done" for all days during the Treatment Period. If the subject is exited from the study due to the 125th event occurring reporting zero PGTCS or "not done" for all days and duration of the Treatment Period is < 166 days, then the subject has not achieved seizure-free status for PGTCS.

A subject will have seizure free status=yes for all generalized seizure types for the applicable Treatment Period if the subject completed the Treatment Period and reported zero generalized seizures for all days during the Treatment Period when the number of generalized seizures was available, and had <10% of days during the Treatment Period with seizure data reported as "not done".

Seizure-free statuses will be calculated for 6-week Titration Period, first 12 weeks of the Treatment Period and the 24-week Treatment Period.

8.3.1.4 Variable: Responder status – reduction in PGTCS frequency

Response to treatment will be based on the percent change in PGTCS frequency, calculated as described in Section 8.3.1.1 . A 50% responder is defined as a subject experiencing ≥50%

reduction in PGTCS frequency per 28 days from the Combined Baseline to the period of interest (6-week Titration Period, first 12 weeks of the Treatment Period or the 24-week Treatment Period). A 75% responder is defined as a subject experiencing ≥75% reduction in PGTCS

Variable: PGTCS frequency - worsening

Seizure worsening is defined as a subject experiencing ≥50% increase in PGTCS frequency per 28 days from Combined Baseline to the period of interest (6-week Titration Period, first 12 weeks of the Treatment Period or the 24-week Treatment Period).

8.3.1.6 Variable: Response.

Variable: Responder status – reduction in days with absence seizures

Response to treatment for absence seizures per 28 days will be based on the percent change in days with absence seizures, calculated as described in Section 8.3.1.2. A 50% responder is defined as a subject experiencing ≥50% reduction in days with absence seizures per 28 days from the Prospective Baseline to the period of interest (6-week Titration Period, first 12 weeks of the Treatment Period or the 24-week Treatment Period). A 75% responder is defined as a subject experiencing ≥75% reduction in days with absence seizures per 28 days from the Prospective Baseline to the period of interest (6-week Titration Period, first 12 weeks of the Treatment Period or the 24-week Treatment Period).

Variable: Responder status – reduction in days with myoclonic 8.3.1.7 seizures

Response to treatment for myoclonic seizures per 28 days will be based on the percent change in days with myoclonic seizures, calculated as described in Section 8.3.1.2. A 50% responder is defined as a subject experiencing ≥50% reduction in days with myoclonic seizures per 28 days from the Prospective Baseline to the period of interest (6-week Titration Period, first 12 weeks of the Treatment Period or the 24-week Treatment Period). A 75% responder is defined as a subject experiencing ≥75% reduction in days with myoclonic seizures per 28 days from the Prospective Baseline to the period of interest (6-week Titration Period, first 12 weeks of the Treatment Period or the 24-week Treatment Period).

Variable: Days with absence and myoclonic seizures - worsening 8.3.1.8

Safety of the LCM treatment will be based on the percent change in days with absence seizure per 28 days and days with myoclonic seizure per 28 days. The increase in days with absence seizures per 28 days from Prospective Baseline will be categorized as >0 to 25%, >25 to 50%, >50 to 75%, and >75% for the Treatment Period. The increase in days with myoclonic seizures per 28 days from Prospective Baseline will be categorized as >0 to 25%, >25 to 50%, >50 to 75%, and >75% for the Treatment Period.

